### Summary Table of Study Protocol

Title	ProSpective Multicenter Observational Study on the Quality of Life of mCRC RAS Wild-type Patients Receiving Anti-EGFR MAb + FOLFOX or FOLFIRI as 1 st Line of Treatment
Protocol version identifier	20140383 Protocol Amendment, Version 2.0
Date of last version of the protocol	10 May 2017
EU Post Authorization Study (PAS) Register No	NA
Active Substance	Panitumumab
Medicinal Product	Vectibix®
Product Reference	EMA/H/C/000741
Procedure Number	EU/1/07/423
Joint PASS	NA
Research Question and Objectives	To assess the impact of the treatment with FOLFOX or FOLFIRI plus anti-EGFR MAb on patients' health related quality of life (HRQoL), as measured by means of the EORTC – QLQC30 questionnaire.
Country(ies) of Study	Italy
Author	PPD Amgen S.r.l. [name]

### Study Design Schema

Approved

## 2. List of Abbreviations

Abbreviation or Term	Meaning
AE	Adverse Event
ALT	Alanine aminotransferase
AST	Aspartate aminotransferase
BMI	Body Mass Index
BSA	Body Surface Area
DBP	Diastolic Blood Pressure
DLQI	Dermatology Life Quality Index
ECOG	Eastern Cooperative Oncology Group
ECG	Electrocardiogram
eCRF	Electronic case report form
EGF	Epidermal growth factor
EGFR	Epidermal growth factor receptor
HRQoL	Health related quality of life
ICF	Informed Consent Form
ICH GCP	International Committee for Harmonization Good Clinical Practice
ICJME	International Committee of Medical Journal Editors
IRB/IEC	Institutional Review Board/ Institutional Ethics Committee
MAbs	Monoclonal Antibodies
mCRC	Metastatic colorectal cancer
QoL	Quality of Life
RAS	Rat Sarcoma Virus
PRO	Patient reported outcomes
SBP	Systolic Blood Pressure
SAE	Serious Adverse Event
WT	Wild type

Approved

### 3. Responsible Parties

Not Applicable

### 4. Abstract

- Study Title

Prospective multicenter observational study on the Quality of life of *RAS* wild-type mCRC patients receiving Anti-EGFR MAb + FOLFOX or FOLFIRI as 1st line of treatment.

- Study Background and Rationale

Cetuximab and Panitumumab are anti-EGFR monoclonal antibodies (MAbs) indicated for the first-line treatment of *RAS* wild-type metastatic colorectal cancer (mCRC) in combination with chemotherapy doublets. Although these drugs have a more targeted and specific action on tumour cells than conventional cytotoxics, they are not devoid of side effects. In particular, cutaneous effects are frequent (50-90%) and sometimes severe. While a relevant amount of safety results have been provided by controlled clinical trials, less evidences about the incidence of adverse events and their management in the real-life scenario have been provided. Moreover, only a few data are currently available about the impact of upfront doublets plus anti-EGFR MAb on patients' quality of life.

- Research Question and Objective(s)

- Primary Objective(s):

- To assess the impact of the treatment with FOLFOX or FOLFIRI plus anti-EGFR MAb on patients' health related quality of life (HRQoL), as measured by means of the EORTC – QLQC30 questionnaire.

- Secondary Objective(s):

- To investigate the impact of dermatological adverse events during the treatment with FOLFOX or FOLFIRI plus anti-EGFR MAb on patients' skin satisfaction as measured by means of the Dermatology Life Quality Index (DLQI) questionnaire.
- To assess the tolerability of administered treatments
- To describe the adherence to the treatment in terms of dose delays, dose reductions, number of administered cycles, average relative dose intensity of every drug.
- To describe the management of dermatological adverse events.
- To assess the effect on skin-related QoL of preemptive vs reactive treatment of skin toxicities.
- Hypothesis(es)/Estimation
- No formal hypothesis will be tested in this study.

Approved

- Study Design/Type

National, multicentric, prospective, observational trial.

- Study Population or Data Resource

RAS wild-type metastatic colorectal cancer patients candidate to first-line FOLFOX or FOLFIRI + anti-EGFR MAb as per clinical practice in around 33 Italian Centers in about **50 months of enrollment (approximately between November 2015 and December 2019)**.

- Summary of *Subject* Eligibility Criteria

Inclusion criteria:

- Adult ( $\geq$  18 years old) RAS wild-type metastatic colorectal cancer patients candidate to receive FOLFOX or FOLFIRI plus Panitumumab or FOLFOX or FOLFIRI plus cetuximab as upfront treatment as per clinical practice.
- Willingness and ability to comply with the protocol
- Written informed consent to study procedures

Exclusion criteria:

- Patients receiving a treatment under clinical investigation may not be included in the study.
- Previous treatment with an anti-EGFR monoclonal antibody.

- Follow-up

Not applicable

- Variables and end-point

- *Outcome Variable(s)*

HRQoL will be measured using the EORTC QLQ-C30 questionnaire. EORTC QLQ-C30 scores reported during the treatment will be also expressed as percentage of the scores reported at baseline.

Skin satisfaction will be measured using the DLQI. The DLQI score will also be expressed as a percentage of the maximum possible score of 30. DLQI scores reported during the treatment will be also expressed as percentage of the DLQI scores reported at baseline.

Tolerability: The toxicity rate, defined as the percentage of patients, relative to the total of enrolled subjects, experiencing a specific adverse event of any grade, according to National Cancer Institute Common Toxicity Criteria (NCI CTC-AE version 4.0), will be reported. Times to onset of dermatological toxicities will be also described.

Management of dermatological toxicity: concomitant medications, both topical and systemic, adopted to prevent or treat dermatological adverse events will be recorded.

- *ExposureVariable(s)*

Treatment adherence: The percentage of delayed cycles, the percentage of cycles administered with reduced doses, the number of administered cycles, the median treatment duration and the average relative dose intensity of every planned drug will be reported.

- Study Sample Size

The sample size calculation is based on feasibility considerations.

A total sample size of 300 patients (10-12 pts/center) has been planned for this study: it is estimated that about 50% (150 pts) of them should be able to complete the QoL questionnaires during the whole treatment period. This population is estimated relevant from the scientific board and useful for a first evaluation on variability of QoL during the follow-up.

- Data Analysis

All recorded parameters will be described: absolute frequency and percentage will be calculated for qualitative variables, while mean, standard deviation, median, first and third quartile will be used to summarize quantitative variables.

To reach the primary endpoint, comparison between the QoL scores (total and partials) at different times will be done and differences in mean from basal and follow-up times will be tested with T-test (Student T-test) paired data.

Tolerability and compliance to treatments, adverse events and their management during the observational period will be described. Their effect on QoL will be evaluated with a multivariate analysis (Anova).

The level of significance will be set to  $p < 0.05$ .

Approved

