## 9. Research Methods

### 9.1 Study Design

This is a national, multicentric, prospective, observational trial. The decision to prescribe FOLFOX or FOLFIRI plus panitumumab or FOLFOX or FOLFIRI plus cetuximab must have been freely taken by the clinician prior to the study entry for each patient included. Each physician will see his/her patients within the context of routine visits, without any special visit being organized for the purposes of the study. Therefore, the doctor-patient relationship and patient follow-up are not modified. Physicians are totally free to decide on their patients' therapeutic management.

EORTC QLQ-C30 and DLQI questionnaires will be completed by the patients at baseline (Day 1 of Cycle 1), at the first day of every other cycle (every 2 weeks) thereafter, and at "End of Study Visit" (within 28 days from the end of treatment with anti-EGFR or withdrawal from study for any reason).

Before every cycle, adverse events will be recorded and graded according to NCI CTCAE Version 4.0. Treatment's modifications in terms of cycles' delay, dose reductions or drugs' interruptions will be recorded. Concomitant approaches to prevent or treat dermatological toxicities during the treatment will be registered.

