### 9.3.2 Outcome Assessment

HRQoL will be measured using the EORTC QLQ-C30 questionnaire. The EORTC QLQ-C30 includes 5 functional scales (physical, role, emotional, social, and cognitive functioning), 3 symptom scales (fatigue, pain, and nausea and vomiting), a global health status scale, and a number of single items assessing additional symptoms (dyspnea, sleep disturbances, constipation, and diarrhea), and perceived financial impact. For the majority of the EORTC QLQ-C30 items a 4-point Likert-type response scale is used. The only exception is the global health status/QoL scale in which a 7-point Likert-type scale is used. For ease of interpretation, all scales and individual item responses are linearly converted to a 0 to 100 scale. EORTC QLQ-C30 scores reported during the treatment will be also expressed as percentage of the scores reported at baseline.

Skin satisfaction will be measured using the Dermatology Life Quality Index (DLQI). The DLQI questionnaire includes 10 questions scored from 0 (not at all, not relevant, not answered) to 3 (very much). The DLQI score is calculated by summing the scores of each question resulting in a minimum of 0 and a maximum of 30. A higher score means an impairment of the quality of life. The DLQI score will also be expressed as a percentage of the maximum possible score of 30. DLQI scores reported during the treatment will be also expressed as percentage of the DLQI scores reported at baseline.

Tolerability: The toxicity rate, defined as the percentage of patients, relative to the total of enrolled subjects, experiencing a specific adverse event of any grade, according to National Cancer Institute Common Toxicity Criteria (NCI CTC-AE version 4.02 ), will be reported. Times to onset of dermatological toxicities will be also described.

Treatment adherence: The percentage of delayed cycles, the percentage of cycles administered with reduced doses, the number of administered cycles, the median treatment duration and the average relative dose intensity of every planned drug will be reported.

Management of dermatological toxicity: concomitant medications, both topical and systemic, adopted to prevent or treat dermatological adverse events will be recorded.

Approved

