### 9.3.3 Covariate Assessment

*Not applicable*

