#### **9.7.2.1 General Considerations**

All recorded parameters will be described: absolute frequency and percentage will be calculated for qualitative variables, while mean, standard deviation, median, first and third quartile will be used to summarize quantitative variables.

The population will be analyzed totally and stratified for treatment (FOLFOX plus panitumumab and FOLFOX plus cetuximab).

The level of significance will be set to  $p < 0.05$ . No interim analyses are planned for this study.

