#### **9.7.2.4 Analysis of the Primary, Secondary, and Exploratory Endpoint(s)**

To reach the primary endpoint ("To assess the impact of the treatment with FOLFOX or FOLFIRI plus anti-EGFR MAbs on patients' health related quality of life"), comparison between the QoL scores (total and partials) at different times will be done and

differences in mean from basal and follow-up times will be tested with T-test (Student T-test) paired data.

EORTC-QLQ C30 score will be calculated in the total population and also in the two subgroups: FOLFOX/FOLFIRI plus panitumumab and FOLFOX/FOLFIRI plus cetuximab.

Differences in mean between the two subpopulation will be tested at different times with T-test.

- To investigate the impact of dermatological adverse events during the treatment with FOLFOX or FOLFIRI plus anti-EGFR MABs on patients' skin satisfaction will be calculated the Dermatology Life Quality Index (DLQI) score.

Differences in mean between the two subpopulation will be tested at different times with T-test.

- To assess the tolerability of administered treatments, Tolerability and compliance to treatments will be described. Their effect on QoL will be evaluated with a multivariate analysis (Anova).
- To describe the adherence to the treatment **with antiEGFR** in terms of dose delays, dose reductions, number of administered cycles, average relative dose intensity of every drug, all these parameters will be described and the single values observed will be compared with the values reported previously, to determine variations .
- Every adverse event occurred will be described with particular attention to dermatologic ones: description, severity and management of the event will be illustrated. Correlation with number of event and treatments (FOLFOX/FOLFIRI plus panitumumab and FOLFOX/FOLFIRI plus cetuximab) will be verify with a multivariate analysis (Anova)
- Will be verified the presence of preemptive treatment of skin toxicities, and events of skin toxicities . The correlation between events of skin toxicities, QoL and presence of preemptive treatment will be tested with a multivariate analysis (Logistic)

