#### **9.7.2.5.3 Sensitivity Analysis for Residual Confounding and Bias**

Not applicable

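### The ANOVA of tolerability and compliance on QoL names no baseline term, so QoL differences present before treatment can be misattributed to those factors

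*Combined protocol and SAP*

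**What the plan says.** The abstract (section 4, Data Analysis) lists tolerability and compliance, adverse events and their management, then states: "Their effect on QoL will be evaluated with a multivariate analysis (Anova". Section 9.7.2.4 repeats the analysis for a shorter list: "Tolerability and compliance to treatments will be described. Their effect on QoL will be evaluated with a multivariate analysis (Anova". There, adverse events appear only in separate analyses: an ANOVA of number of events by treatment, and a logistic model for skin toxicity, QoL and pre-emptive treatment.

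Neither place gives the model terms, the form of the QoL outcome, the visit, or the factor levels. Two sections where adjustment might be described, "9.3.3 Covariate Assessment" and "Sensitivity Analysis for Residual Confounding and Bias", are both marked as not applicable. Appendix A lists no stand-alone documents, so the plan points to no separate SAP that could supply the model.

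Baseline data exist. Section 9.1 states: "EORTC QLQ-C30 and DLQI questionnaires will be completed by the patients at baseline (Day 1 of Cycle 1". The Baseline list in section 9.3 adds ECOG. Baseline QoL is used in two other ways. Section 9.3.2 says: "EORTC QLQ-C30 scores reported during the treatment will be also expressed as percentage of the scores reported at baseline". The primary analysis in 9.7.2.4 says: "differences in mean from basal and follow-up times will be tested with T-test (Student T-test) paired data". Neither is tied to this ANOVA.

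**The concern.** Having an adverse event, a delayed cycle or a reduced dose is observed after treatment starts; nobody is allocated to it. Section 9.1 leaves management entirely to the physician. Patients who start in poorer condition may plausibly have more events and dose modifications, and may also start with worse QLQ-C30 scores. An ANOVA of on-treatment QoL on these factors alone would compare groups that could already differ on Day 1 and describe the difference as an effect of the factor.

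There is also a loss that needs no confounding. Baseline QoL usually predicts later QoL. If it is left out, the variance it explains stays in the error term, and the interval is wider than the collected data require. That matters in a study that expects full questionnaire completion from only about half its patients.

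**Working it through.** **Inputs from the documents.** Planned N is 300, of whom 50% are expected to complete the questionnaires throughout (section 9.5): 300 × 0.50 = 150, which reproduces the plan's figure. On the test level, section 9.7.2.1 says "The level of significance will be set to" p < 0.05; I take this as two-sided. Cutaneous effects are put at 50-90% of patients (sections 4 and 7), and dermatologic events of any grade at more than 90% with panitumumab (section 7.1). There is no power calculation to reproduce.

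**Assumptions, not in the documents.** SD 20 points; baseline-to-visit correlation r = 0.4 to 0.6; no true effect; baseline gap of 5 points (8 as a worse case); share of patients with the event p = 40% or 90%. On-treatment scores regress on baseline in the same way in both groups.

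**Raw score as outcome.** Spurious difference = r × gap.
- 5-point gap: 0.4 × 5 = 2.0 to 0.6 × 5 = 3.0 points.
- 8-point gap: 3.2 to 4.8 points.

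SE = 20 × √(1/(np) + 1/(n(1−p))).
- n=150, p=40%: 20 × √(1/60 + 1/90) = 3.33.
- n=150, p=90%: 20 × √(1/135 + 1/15) = 5.44.

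False-positive rate = Φ(b/SE − 1.96) + Φ(−b/SE − 1.96), where b is the spurious difference.

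| n | event share | 5-point gap | 8-point gap |
|---|---|---|---|
| 150 | 40% | 9-15% | 16-30% |
| 150 | 90% | 7-9% | 9-14% |
| 300 | 40% | 14-25% | 27-53% |
| 300 | 90% | 8-12% | 13-24% |

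With no gap the rate is 5%.

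**Change from baseline as outcome.** The bias is (1 − r) × gap with the opposite sign: at a 5-point gap, +3.0 (r = 0.4) to +2.0 (r = 0.6). The group that started worse appears to fare better.

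**Percent of baseline as outcome.** In a simulation (4,000 runs, n=150, equal groups, baseline mean 65, SD 20, r = 0.5, scores bounded), a 5-point gap gave a spurious +6.7 percentage points and 13% false positives. The raw score gave −2.5 points and 12%; ANCOVA gave about 0 and 5%. Percent of baseline is also undefined when the baseline score is 0, which the DLQI and the 0-100 symptom scales allow.

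**Precision with no gap.** Baseline adjustment multiplies the SE by √(1 − r²): √0.84 = 0.917 at r = 0.4 and √0.64 = 0.80 at r = 0.6, a cut of 8% to 20%. In patients this is 1/(1 − r²) = 1.19 to 1.56, or 19% to 56% more.

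**Limit of the adjustment.** The null result for ANCOVA depends on the data model above. If instead a 5-point gap simply persists on treatment with no event effect, the raw comparison gives −5, ANCOVA gives −5 × (1 − r) = −3.0 to −2.0, and change gives 0. ANCOVA is still better than the raw comparison, but it is not a cure.

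**The case against.** The strongest reply is that the plan is silent and does not exclude baseline. A reader might infer from section 9.3.3 that covariates were deliberately ruled out. The documents do not support that. The same entry stands under Baseline Period (9.2.5) although baseline assessments are listed in 9.3, under Stratified Analysis although 9.7.2.1 stratifies by treatment, and under safety analysis (9.7.3) although 9.7.2.4 analyses adverse events. It is template text used loosely. This stands: the point is that no term is named, not that baseline is forbidden.

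A reader might also infer that the analysis will overstate the harm of toxicity. That is not established either. It needs a baseline gap, for which the documents give no figure, and a raw-score outcome, which the plan does not state. Change or percent of baseline can reverse the sign.

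The size is assumption-bound. A 40% event share sits poorly with tolerability defined by events of any grade and skin events of 50-90% or more; at 90% the inflation is small. Dose delays or reductions could be less frequent, but the documents give no rate.

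Finally, section 7.3 declares the study descriptive with no inference planned. This lowers the weight of the false-positive rates but does not answer the point: the plan still sets a significance level and evaluates an effect, and a descriptive label does not remove confounding from the estimate. The paired t-test does not help, because it is a within-patient analysis of another question.

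**Conclusion.** The concern holds in a limited form. The plan evaluates the effect of non-assigned factors on QoL without naming any baseline term, although baseline QLQ-C30 and ECOG are collected. Pre-treatment differences can therefore be misattributed, in a direction that depends on an outcome still to be defined. For a 5-point baseline gap and raw scores at n=150, the illustration is a spurious 2 to 3 points, with a false-positive rate of about 9-15% (40% with the event) or 7-9% (90%). This rests on an assumed SD, correlation, gap and event share. The precision argument does not need a gap: the SE can be cut by about 8-20% at correlations of 0.4 to 0.6. Because this is a secondary analysis in a study declared descriptive, severity is low to moderate.

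**What to change.** In the abstract and in section 9.7.2.4:
- Use the same list of factors in both places, and say whether adverse events and their management belong in this model.
- Name the on-treatment QLQ-C30 score as the outcome, and name the time point.
- Replace the ANOVA by an ANCOVA, or a mixed model if visits are pooled, with the patient's baseline score on the same scale and baseline ECOG as covariates.
- Describe the results as associations adjusted for baseline, not as effects. Adjustment does not remove other confounding, toxicity that accrues over time, or dropout (about half the patients are expected not to complete the questionnaires throughout, and nothing is imputed).

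In section 9.3.3, list the two covariates in place of the current entry.

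The cost is wording only; the data are already collected. The downside is that patients without a baseline form drop out of this model, as they already do from the paired primary analysis.

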## 5. Amendments and Updates

### Protocol version 2 24Oct 2019

Section	Text in Protocol	Amended Text	<<Rationale for Change>>
Global			Template used 14.0 20 May 2019
Summary Table of study Protocol/ Page 1	Protocol version identifier	Replace: 20140383 Version Amendment 1 With: 20140383 Protocol Version 2	New version of the protocol
Summary Table of study Protocol/ Page 1	Date of last version of the protocol	Replace: dated 10 May 2017 With: dated 24 Oct 2019	Last version of the protocol amendment
Section Investigator Agreement, page 3	Title to match with the cover page and Amendment date	Replace: dated 10 May 2017 With: protocol ProSpective multicenter observational study on the Quality of life of mCRC RAS wild-type patients receiving Anti-EGFR MAbs + FOLFOX or FOLFIRI as 1st line of treatment dated 24 Oct 2019	Title to match with the cover page and new version of the protocol amendment
Table of contents	9.2.4 matching 9.2.5 baseline Period 9.2.6 Study Follow up		New sections in the template
Table of contents	9.9.1 Information Bias	9.9.1 Internal Validity of Study Design: Information Bias	New template
Section 4. Abstract Title Study Population or Data Resource	Section 4 Study Population or Data Resource	Replace: 38 months of enrollment (approximately between November 2015 and December 2018). With: 50 months of enrollment (approximately between November 2015 and December 2019).	New study timelines
Section 5. Amendments and Updates	Table with the amendment changes	Add: changes of amendment 2 protocol Add all the former protocol versions	Changes of the protocol amendment
Section 6. Milestones	New study milestones	Replace: end of data collection and final report of study results With: End of data collection: 1 o Quarter 2021. Final report of study results: 4 o Quarter 2021	New study milestones with the adjustment plan

Approved

Section	Text in Protocol	Amended Text	<<Rationale for Change>>
Section 7 rationale and background	These results will probably help clinicians to become more and more confident with respect to the adoption of these combinations in their routinary activity	These results will probably help clinicians to become more and more confident with respect to the adoption of these combinations in their routinely activity	Grammatical error
Section 9.2.1 Study Period	Months to enroll	Replace: 38 months With 50 months	New study milestones with the adjustment plan
Section 9.2.1 Study Period	End of study dates	Replace: will end approximately in Dec 2018. The end of study is planned for December 2019 With: will end approximately in December 2019. The end of study is planned for December 2020	New timelines for the enrollment period and end of study.
Section 9.3: End of study		Add : or reaching cycle 56	New decision to end the study
Section 9.3.1 Exposure Assessment	The percentage of delayed cycles, the cycles administered with reduced dose, the number of administered cycles, the median treatment duration and the average relative dose intensity of every planned drug will be reported	The percentage of delayed cycles, the cycles administered with reduced dose, the number of administered cycles, the median treatment duration and the average relative dose intensity of anti-EGRF drug will be reported	No single information required, just general information
9.4 Data sources	Utilising	Utilizing	Grammatical error
9.7.2.4 Analysis of the Primary, Secondary and Exploratory Endpoints	To describe the adherence to the treatment in terms of dose delays, dose reductions, number of administered cycles, average relative dose intensity of every drug, all these parameters will be described and the single values observed will be compared with the values reported previously, to determine variations .	To describe the adherence to the treatment with antiEGFR in terms of dose delays, dose reductions, number of administered cycles, average relative dose intensity of every drug, all these parameters will be described and the single values observed will be compared with the values reported previously, to determine variations .	No single information required, just general information

Approved

Section	Text in Protocol	Amended Text	<<Rationale for Change>>
9.9.1 Internal Validity of Study Design: Information Bias	Information Bias	Internal Validity of Study Design: Information Bias	New title
Section 10.4 Subject Decision to Withdraw	Subject Decision to Withdraw	Add subjects decision to withdraw	New text required
Section 11.1.2 Serious Adverse Events		Add subject /patient	New text required
Section 11.1.3 Other Safety Findings	NA	Add bullets to the description	Bullets inserted
Section 11.2 Safety requirements	The investigator is responsible for ensuring that safety events (adverse events, product complaints and other safety findings) observed by the investigator or reported by the patient that occur after signing of the informed consent form through the final study contact are recorded in the patient's appropriate study documentation. Safety events must be submitted as individual case safety reports to Amgen via the applicable Amgen Safety Reporting Form (paper) within 1 business day of investigator awareness. Safety events that are not reported as part of this study or suspected to be related to any medicinal product other than the Vectibix® should be reported to the local authority in line with the local country requirements.	This study is prospectively collecting information of enrolled patients. All safety events (adverse events, product complaints, and other safety findings) considered to have occurred following subject exposure to anti-EGFR will be collected from signing of the informed consent form to the final study contact. The investigator is responsible for recording safety events that they become aware of during study period in the patient's appropriate documentation. Collected safety events occurred after subject exposure to panitumumab, with the exception of the protocol-exempted events listed in the section below, must be submitted as individual safety reports to Amgen via the applicable Amgen Safety Reporting Form (paper form) within 1 business day of investigator awareness.	New text according to new version
Section 11.2 Safety requirements	The Investigator may be asked to provide additional information for any event submitted, which may include a discharge summary or extracts from the medical record. Information provided about the event must be consistent with information recorded on the study Case Report Forms (CRFs) documentation where safety data may also be recorded (eg.: Event CRF).	The Investigator may be asked to provide additional information for any event submitted, which may include a discharge summary or extracts from the medical record. Information provided about the event must be consistent with information recorded in the study documentation where safety data may also be recorded (eg.: Case Report Form, CRF).	Grammatical changes

Approved

Section	Text in Protocol	Amended Text	<<Rationale for Change>>

Section 11.2.1            Protocol            exempted            Safety            Information
	
Non serious adverse events related to anti-EGFR (Vectibix® or Cetuximab®): skin and nails disorders and hypomagnesemia.
	
Regardless of causality, for this study all safety events experienced by the subjects exposed to panitumumab must be reported to Amgen within 1 business day of investigator awareness with the exception of the following non serious adverse events related to anti-EGFR and induced by chemotherapy as listed below:
 
 
• Non serious adverse events related to anti-EGFR (Vectibix®):              skin and nails disorders and hypomagnesemia.
 
• Non serious adverse events induced by chemotherapy:              anemia, neutropenia, neurotoxicity, diarrhea.
 
 
The rationale for exempting the above non serious events from reporting to Amgen within 1 business day is that the safety profile of panitumumab, and chemotherapies are fully described in the respective Summary of Product Characteristics. If any of the exempted events have a fatal outcome, they should be considered a serious adverse event and must be reported individually within 1 business day of investigator awareness.
 
All safety information that is not specified in this section including all fatal events are to be collected and submitted to Amgen within the specified time frame.
 
Protocol-exempted events and safety events that are suspected to be related to any medicinal product other than panitumumab should be reported to the local authority in line with the local country requirements.
	
This is an observational study and the AE occurred in patients treated with Cetuximab are being collected and recorded into the database, but they must not be sent to Amgen Safety.

Approved

Section	Text in Protocol	Amended Text	<<Rationale for Change>>
Section 13.1 Publication Policy	NA	Add bullets to the description	Bullets inserted
Appendix B	NA	New version 4.0 of template Sample Safety Reporting Form (067756) uploaded	New updated version
Appendix D	NA	New version 1 of template 115199 and 115201 (pregnancy and lactation notification form)	New updated versions

